#### APPROACH:

#### **RESEARCH DESIGN AND METHODS:**

**Study design:** High-fidelity simulation experiments performed using three transmissionbased precaution scenarios.

**Study eligibility:** HCP will be recruited for participation in the experimental assessments. The target sample size is 150 subjects with an explicit goal for a diversity of HCP types (i.e. physicians, nurses, and house staff). Eligible subjects must be currently working in a healthcare setting. Because the intricacies of EVD-specific precautions, for the scenarios focused on this type of precautions, volunteers will be recruited from members of the Vanderbilt Communicable Disease Response Team (CDRT). The CDRT consists of HCP from the following disciplines: nurses, physicians (including Epicenter Investigators [name] and [name]), paramedics, and educators. Each team member possesses knowledge and/or skills necessary to care for patients who require intensive medical care. Each volunteer also receives intensive periodic (quarterly) training in the care of patients with highly communicable, serious infectious diseases. Training includes specific disease pathology, PPE use, and EVD infection prevention protocols. Participants will be paid for participation in this study.

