## Study procedures:

Three transmissionbased precaution scenarios will be utilized (Table 2). These will involve Contact Precautions (PPE: gown and gloves), Droplet Precautions (PPE: surgical mask), and EVD-Precautions (PPE: PAPR, eve protection, hood, aown. double aloves. lea

coverings, and apron). For the Contact Precautions scenario, subjects will perform a brief history and abbreviated physical exam along with a simulated wound dressing change. For the Droplet Precautions scenario, subjects will perform a brief history and abbreviated physical examination along with management of a urinary catheter (including emptying of collection bag). For the EVD-Precautions scenario, subjects will perform a brief history and abbreviated physical exam along with medication administration through an intravenous catheter. Non-CDRT personnel will participate in both the Contact and Droplet scenarios (A-D in Table 2), while only CDRT members will participate in the EVD-Precautions scenario (E & F in Table 2). Each

scenario will have a standard 10 minute duration and a prolonged 20 minute duration (in which the exam is a standard physical exam) to assess the impact of prolonged PPE use on compliance.

Using a fluorescent compound to reproduce contaminants in assessing

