#### Study outcomes and assessment:

1) Lapses in PPE use: These will be captured via video monitoring and recording of each subject experiment from PPE donning through PPE doffing. Two independent investigators will review every scenario and note the frequency and type of breaches in the use of PPE. Investigators will be trained on a standardized method for reviewing each scenario and will use a standardized abstraction tool. The time of the lapse in relation to scenario start will be captured to examine the impact of the duration of PPE use.

2) HCP and environmental contamination: Contamination will be assessed using ultraviolet light inspection of the subjects following doffing of PPE and of the simulation room environment to assess for the number of contamination events during each scenario. The rooms will be cleaned prior to each experiment to avoid cross-contamination.

**Analysis:** A descriptive analysis of the frequency (number per minute of scenario time), number, and types of lapses in PPE use will be performed. The number of self and environmental contamination events (defined as an identified patch of fluorescent powder located in these areas) will also be described as a quantitative number and an event rate per minute of scenario time. Lapse and contamination rates will be compared between each scenario type (Contact, Droplet, and EVD), scenario duration (standard vs. prolonged), and HCP type (physician, nurse, other) using Student's t-test or Wilcoxon Rank Sum test (for duration comparison) and ANOVA or Kruskal-Wallis analysis (for precaution type and HCP type comparison given >2 study groups). For categorical outcomes (e.g. the number of lapses) Fisher's Exact Test will used for comparisons.

**Limitations:** Even with a larger study cohort, the sample size will limit the ability to examine nuanced details in patient care while wearing PPE that lead to lapses. Nonetheless, this will be one of the largest and most complex simulation experiments on PPE use published to date.

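### Aim I's pooled, one-factor test of HCP type can mix profession with EVD equipment and CDRT training, above all for the residual "other" group

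*Protocol*

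**What the plan says.** All references are to the Protocol, Specific Aim I.

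- **Study eligibility.** Recruitment: "The target sample size is 150 subjects with an explicit goal for a diversity of HCP types", and the types listed are physicians, nurses and house staff. The entry rule itself is wider: "Eligible subjects must be currently working in a healthcare setting". Volunteers for the EVD scenarios come from the Communicable Disease Response Team (CDRT): "The CDRT consists of HCP from the following disciplines: nurses, physicians", and also "paramedics, and educators". The team trains intensively every quarter, including on PPE.
- **Study procedures.** Non-CDRT staff do the Contact and Droplet scenarios (A to D), while "only CDRT members will participate in the EVD-Precautions scenario (E & F in Table 2"). The equipment differs widely: gown and gloves for Contact, a surgical mask for Droplet, and seven listed components for EVD.
- **Study outcomes and assessment, Analysis.** Rates are compared by scenario type, by duration and by "HCP type (physician, nurse, other"). The test for HCP type is ANOVA or Kruskal-Wallis. Each factor is listed as its own comparison, and no stratification or adjustment by precaution type is stated for the HCP-type test.

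**The concern.** Aim I exists to find risk factors for self-contamination, and HCP type is one of the three factors it compares. The results are meant to inform the Aim II audit tool. Precaution type is another of the three factors, so the plan itself expects that outcomes may differ by it. It is also tied to who the subject is, because EVD runs come only from CDRT members, and the CDRT has its own mix of professions. A one-factor test pooled over all runs cannot separate profession from EVD equipment and CDRT training. An apparent profession effect could be a scenario effect, and a real one could be masked.

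**Working it through.** No figure in the plan bears on this. Aim I gives a target of 150 subjects with no split by HCP type or CDRT status, and no effect size or variance. The check is therefore a comparison of the sections, plus one identity.

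**1. Who can be in each analysis group**

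| Analysis level | Named sources | Scenarios |
|---|---|---|
| Physician | Recruited physicians; CDRT physicians; perhaps house staff | A–D and E–F |
| Nurse | Recruited nurses; CDRT nurses | A–D and E–F |
| Other | CDRT paramedics and educators; perhaps house staff; perhaps other eligible staff | E–F, plus A–D if the last two are included |

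**2. Where house staff go.** The text does not say, so there are three cases.

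- (a) House staff count as physicians and the recruitment list is closed: the residual level holds only CDRT paramedics and educators.
- (b) House staff count as other: the level pools house staff from Contact and Droplet runs with CDRT paramedics and educators from EVD runs.
- (c) The recruitment list is read as examples: the level may also hold non-CDRT staff of other professions in A–D.

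Physicians and nurses exist as groups in all three cases.

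**3. The spurious difference.** Let w be the share of a group's runs that are EVD runs, and Δ the mean outcome in EVD runs minus the mean in Contact and Droplet runs. If profession has no effect, and the Contact/Droplet balance is the same across groups, then

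expected difference (group 1 − group 2) = (w₁ − w₂) × Δ.

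This is zero only if the two EVD shares match or Δ is zero.

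For case (a), suppose also that CDRT members do only EVD runs, so that w = 1 for the residual group. Assumed EVD shares among physicians or nurses then give:

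| Assumed w, physicians or nurses | Spurious difference |
|---|---|
| 0.10 | (1 − 0.10)Δ = 0.90Δ |
| 0.20 | (1 − 0.20)Δ = 0.80Δ |
| 1/3 | (1 − 1/3)Δ = 0.67Δ |
| 0.40 | (1 − 0.40)Δ = 0.60Δ |

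In cases (b) and (c) w for the residual group is below 1, and the artefact shrinks, to nothing if the shares happen to match. Physician versus nurse is affected only as far as their own EVD shares differ.

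**4. Sign of Δ.** Seven EVD components against two for Contact and one for Droplet offer more chances for a lapse. Quarterly CDRT training works the other way. The documents do not settle which dominates.

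**5. Does the per-minute rate help?** No. Every scenario type has the same 10- and 20-minute versions, so dividing by time does not remove a difference due to equipment.

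**The case against.** The case against has real substance.

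- **Recruitment goals need not equal analysis strata.** Assigning house staff and defining the residual level are coding rules that an analysis plan, not shown here, may settle. This stands, and it is why the difference between the two lists is only a minor edit. It does not answer the main point, because the protocol itself names a one-factor test.
- **The residual group need not be CDRT-only.** Eligibility covers anyone working in healthcare. The procedures also limit who does EVD runs without stating that CDRT members do nothing else. Both points stand, so a reader who infers that the residual group is fully aliased with EVD goes further than the text.
- **A mixed residual group is ordinary, and the physician-versus-nurse contrast survives.** This stands too. A reader might conclude that the HCP-type result is uninterpretable, and the documents do not support that.
- **A large artefact cannot be read off the equipment lists.** A reader might assume eight EVD items with a 25% lapse chance each. That gives 8 × 0.25 = 2.0 lapses, against (0.5 + 0.25)/2 = 0.375 for Contact and Droplet, a ratio of 5.3. But the section lists seven components, the 25% is assumed, and CDRT training is ignored. Physicians and nurses also do EVD runs. If these are one fifth of their runs, their mean is 0.8 × 0.375 + 0.2 × 2.0 = 0.70 and the ratio is 2.9. At one third it is 0.92 and 2.2. No such figure should be quoted as the size of the problem.
- **Aim I is largely descriptive, with no declared primary comparison.** True, and it limits the weight of the point.

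**Conclusion.** The point holds as a confounding problem in one stated comparison. Followed as written, the pooled HCP-type test can attribute to profession what belongs to EVD equipment or CDRT training, most plausibly for the residual group. Its size is (difference in EVD share) × Δ. Neither factor can be obtained from the protocol, so magnitude and direction stay open. The conclusion rests on two things in the text: EVD runs come only from CDRT members, and no adjustment for precaution type is stated. It does not depend on how house staff are coded, although that choice changes which contrast is affected most. It is a moderate, cheaply corrected weakness in one of three comparisons and does not invalidate Aim I.

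**What to change.** In the Aim I Analysis paragraph, replace the pooled HCP-type test with a comparison on the Contact and Droplet runs of non-CDRT subjects, with scenario type in the model. Stratifying by precaution type is an acceptable alternative. Because these subjects take part in both scenarios, the model should allow for repeated runs from one person. Report CDRT disciplines descriptively within the EVD runs.

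As a minor accompanying edit, align the HCP-type lists in Study eligibility and Analysis: state where house staff are counted and who forms the residual level, and record profession and CDRT membership at enrolment. A separate house-staff level is optional, since it would give four smaller groups instead of three.

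The cost is a few sentences and at most one or two form fields. The one real loss is that EVD runs drop out of the HCP-type test, so it uses fewer runs. Recruitment, scenarios and outcome measurement do not change.

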In a follow up investigation, this team examined compliance with isolation practices among 24 nurses using a simulated patient care setting. Using methods similar to those noted above, poor compliance with PPE donning, in-room PPE use, and PPE doffing was noted. Example breaches included failure to tie gowns at the neck, touching of the face or other nonprotected areas with contaminated gloves, and failure to doff PPE as per recommendations.

Casanova *et al* compared the use of single vs. double gloving while performing a vital signs assessment on a simulation manikin and the risk of MS2 nonpathogenic bacteriophage contamination of the PPE components and participant hands. Among the 18 HCP volunteers, hand contamination with MS2 was significantly more frequent with the use of a single pair of gloves (occurring in 78% of volunteers vs. only 28% of volunteers when double gloving was utilized, *p* = 0.006). Errors in PPE removal were frequent in both scenarios (72% with any error in double gloving scenarios; 67% in the single gloving scenario). Importantly, contamination occurred even with a visible PPE removal protocol present for reference during the scenario, suggesting the need for additional strategies to improve compliance along with these "just-in-time" reminders.

Lai *et al* examined the risk of contamination with different glove removal techniques using a fluorescent solution. Glove removal using any technique led to environmental contamination. Wong and colleagues identified a variable risk of HCP contamination between different types of PPE (gowns or aprons) using simulated respiratory secretion exposure with a fluorescein solution. A randomized crossover study of 50 subjects wearing novel respiratory pathogen precautions PPE (gloves, gown, N95 particulate respirator, face shield, and hair cover with and without a powered air-purifying respirator [PAPR]) also used fluorescein solution to assess contamination with PPE use. The solution was atomized onto the HCP while in the PPE,

[figure not shown]
mimicking exposure to respiratory droplets. Contamination was greater in those who did not wear the PAPR, with the anterior neck, forearms, wrists and hands the most common areas of contamination.

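### Aim I's rank-sum option does not test equal per-minute rates when runs last 10 or 20 minutes; with sparse events at a constant rate it leans towards finding prolonged PPE use worse

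*Protocol*

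**What the plan says.** In the Protocol, Specific Aim I, Study procedures, each "scenario will have a standard 10 minute duration and a prolonged 20 minute duration", and the longer run is there to show what prolonged PPE use does to compliance.

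The Analysis paragraph under Study outcomes and assessment describes the "frequency (number per minute of scenario time), number, and types of lapses in PPE use", and treats contamination as a number and as an "event rate per minute of scenario time". It then states: "Lapse and contamination rates will be compared between each scenario type", by duration and by type of healthcare worker. For duration, the tests named are "Student's t-test or Wilcoxon Rank Sum test (for duration comparison"). No rule is given for choosing between the two.

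On size, Study eligibility says only: "The target sample size is 150 subjects". Aim I states no significance level, expected event rate or number of runs per duration.

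**The concern.** The two groups have a two-fold difference in exposure by design. Dividing by minutes equalises the mean rates when events are proportional to time, but not the distributions. A 10-minute run can only yield 0, 0.1, 0.2 and so on per minute; a 20-minute run yields 0, 0.05, 0.10 and so on, with fewer zeros. The rank-sum test asks whether a value from one group tends to exceed a value from the other, and for such data the answer is not even odds when the rates are equal. Because the tested null is then false, a larger study makes the error worse.

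This is the comparison meant to show whether longer PPE use leads to more breaches, and Aim I is to inform the audit tool of Aim II. A spurious duration effect could be carried forward.

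**Working it through.** The protocol states no error rate or power for Aim I, so there is no figure of its own to reproduce.

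**Inputs from the protocol.** Run lengths 10 and 20 minutes; rates per scenario minute; 150 subjects.

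**Assumed inputs.** Two-sided 5%, so 2.5% is nominal for a false finding that prolonged use is worse. Poisson counts at a constant rate, with gamma between-subject variation (CV 0.5). Runs per duration: 75 (150 subjects with one run each, 150/2) to 150 (one run at each duration). Mean events per 10 minutes, m, from 0.33 to 8.

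**Anchors for m.** If a share p of subjects has at least one event, a Poisson count has m = −ln(1 − p).
- An earlier simulation cited in Aim I found fluorescent powder on 80% of subjects: −ln(0.20) = 1.6.
- The lower figure in "78% of volunteers vs. only 28% of volunteers when double gloving was utilized" gives −ln(0.72) = 0.33, but this concerns hands only, under double gloves.

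Both assume that the cited runs resemble a 10-minute run.

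**Step 1: what the rank-sum test targets.** With X ~ Poisson(m) over 10 minutes and Y ~ Poisson(2m) over 20, the rates are equal. The test's null is θ = P(Y/20 > X/10) + ½P(tie) = 0.5. Exact values without between-subject variation:
- m = 0.33: 0.354 + ½ × 0.398 = 0.554. Zeros: 72% of 10-minute runs, 52% of 20-minute runs.
- m = 1.6: 0.457 + ½ × 0.131 = 0.523. Zeros: 20% and 4%.
- m = 4: 0.473 + ½ × 0.082 = 0.514.
- m = 8: 0.481 + ½ × 0.058 = 0.510.

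θ exceeds 0.5 in every case.

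**Step 2: false finding that prolonged use is worse** (simulation, 6,000 studies per cell, CV 0.5, equal true rates):

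| m per 10 min | Different subjects, 75 / 150 per duration | Same subjects, 75 / 150 |
|---|---|---|
| 0.33 | 26% / 45% | 24% / 44% |
| 0.5 | 21% / 35% | 20% / 34% |
| 1.6 | 7% / 11% | 4% / 7% |
| 4 | 5% / 6% | 0.5% / 1% |
| 8 | 3% / 4% | 0.1% / 0.1% |

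Separate simulations of the same settings gave 23–45% at 0.33 and 5–12% at 1.6.

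**Step 3: alternatives.**
- Student's t-test on the same rates: total two-sided error about 4–6% with different subjects. With the same subjects it falls to about 0.2–4%, because the pairing is ignored.
- A rate test on the counts with minutes as exposure: 1.8–2.7% for a false finding of worse (independent Poisson counts, m from 0.3 to 3, 37 to 150 per duration). Poisson regression with a log-minutes offset and participant-clustered errors: 4–6% two-sided with CV 0.5.

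**Step 4: events that do not scale with minutes.** Lapses are recorded from donning to doffing. Suppose 0.5 events per run are fixed and 0.5 occur per 10 minutes. The per-minute rates become (0.5 + 0.5)/10 = 0.10 and (0.5 + 1.0)/20 = 0.075, although behaviour in the room is unchanged. The rank-sum test then says worse in 0–0.5% of studies and better in 12–33% (37 to 150 per duration).

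**The case against.** **The size rests on inputs that the protocol does not give.** This stands. The sparse end (0.33) comes from double-gloved hands, whereas Aim I uses double gloves only in the EVD scenario and counts patches anywhere on the person and in the room. The same cited study found 78% with single gloves. For lapses, another cited simulation saw at least one breach in every one of 10 participants; a Poisson mean of 1 would leave e^(−1) = 37% with none, so lapses may lie where the bias is small. A reader might infer that the plan as such carries a false-positive rate of a third or more. The documents do not support that.

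**The direction is not assured.** This also stands. A reader might infer that any error must favour calling prolonged use worse. That holds only for events proportional to time; Step 4 shows the reverse.

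**The t-test is an equal option, and the choice may be settled in an analysis plan.** This stands in part. The defect bites only if the rank-sum test is used, and it cannot be assumed that it would be. But the protocol lists it as acceptable for this comparison without a rule, and skewed, zero-heavy counts are the usual reason for turning to it. The t-test is no full remedy if the same people do both durations, which the assignment of staff outside the response team to scenarios A to D suggests but does not settle.

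**A log-minutes offset applied to everything could do worse.** This stands against a bare offset. With half the events at a mean of 1.6 fixed per run, a clustered Poisson model with offset calls prolonged use better in 52–69% of studies; with a quarter fixed, in 15–22%, against 3–5% for the rank-sum test. The offset is faithful to the per-minute rate that the plan chose, but that rate is not meaningful for once-per-run events.

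**Aim I is exploratory.** It has no stated significance level or confirmatory hypothesis, which limits the consequence but does not make the test fit the question.

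**Conclusion.** The point holds in a conditional form. A rank-sum test on per-minute rates from 10- and 20-minute runs is not a test of equal rates, whatever the event frequency. How much this matters depends on how sparse the events are. Under constant-rate Poisson counts with CV 0.5 and 75 to 150 runs per duration, the false finding that prolonged use is worse occurs in about 20–45% of studies at 0.33–0.5 events per 10 minutes, about 4–12% at 1.6 (the value nearest to the protocol's own cited contamination figure), and about 6% or less at 4 or more, against 2.5% nominal. With the same subjects at both durations and 4 or more events, the unpaired test is conservative instead. A component fixed to donning and doffing can turn the bias round. The wording should be changed before analysis; nothing in the conduct of the study is affected.

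**What to change.** In the Aim I Analysis paragraph, remove the rank-sum option for the duration comparison. Analyse the counts by Poisson or negative-binomial regression with log(scenario minutes) as offset and standard errors clustered by participant, and report the rate ratio of prolonged to standard runs with its confidence interval.

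- **Lapses:** the plan already records when each lapse occurs relative to scenario start. Apply the offset only to lapses within the scenario, and compare donning and doffing lapses as counts per run, without offset.
- **Contamination:** it is inspected only after doffing and cannot be timed. Report the ratio of counts per run without the offset beside the rate ratio, so that readers can see how far the result depends on assuming proportionality to time.

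The cost is a change of wording and slightly more analysis work. No new data are needed.

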#### Table 2: Simulation Scenarios for Aim I

Scenario	Standard Duration (10 mins)	Prolonged Duration (20 mins)				
Contact Precautions	Α	В				
Droplet Precautions	С	D				
EVD-Precautions	E	F				

contamination rate is effective and can be utilized for comparison with body and environmental contamination levels. A fluorescent powder (Glo Germ Co, Moab, UT) especially developed for determining hand hygiene compliance will be used in this study. The powder will be applied in standardized amounts at locations surrounding and on the simulated patient (on patient's upper torso and arms, within the simulated wound for scenarios A & B, on the urinary collection bag for scenarios C & D, on the peripheral IV hub in scenarios E & F, on both bed rails, and on the patient's bedside table) prior to the scenario start. Subjects will be blinded to the locations of powder placement.

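### Aim I analyses repeated runs by the same volunteers with independent-group tests, and its three-way precaution comparison cannot separate EVD precautions from the specially trained team that performs them

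*Protocol*

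**What the plan says.** All references are to the protocol, Specific Aim I.

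- **Sample.** Study eligibility gives a bare target: "The target sample size is 150 subjects with an explicit goal for a diversity of HCP types". The split between CDRT and other volunteers is not stated.
- **Who does what.** Study procedures assigns the first two precaution types as follows: "Non-CDRT personnel will participate in both the Contact and Droplet scenarios (A-D in Table 2"). The third type is reserved for the response team: "only CDRT members will participate in the EVD-Precautions scenario (E & F in Table 2"). Each scenario has a 10-minute and a 20-minute version.
- **Training.** Of the CDRT, Study eligibility says: "Each volunteer also receives intensive periodic (quarterly) training in the care of patients with highly communicable, serious infectious diseases". PPE use is listed among the training topics.
- **Tests.** The Analysis paragraph under Study outcomes and assessment compares lapse and contamination rates by precaution type (Contact, Droplet, EVD), duration and HCP type. It names Student's t-test or "Wilcoxon Rank Sum test (for duration comparison) and ANOVA or Kruskal-Wallis analysis (for precaution type and HCP type comparison"), on the ground that there are more than two groups. It adds: "For categorical outcomes (e.g. the number of lapses"), Fisher's exact test.

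No paired, repeated-measures or mixed method is named. The Limitations paragraph mentions only sample size.

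**The concern.** One non-CDRT volunteer supplies at least two records (Contact and Droplet), and four if scenarios A to D mean that everyone does both lengths. People differ in how carefully they use PPE, so records from one person are correlated. Tests for independent groups ignore this, and the consequence depends on the factor:

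- HCP type varies between people. Counting each run as a separate person makes the standard error too small and produces false positives.
- Contact versus Droplet varies within people. The unpaired test leaves the person-to-person variation in the error term, so the standard error is too large and power is lost. The same holds for duration if each volunteer does both lengths.

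Separately, no one outside the CDRT does EVD, and on the natural reading no CDRT member does Contact or Droplet. A difference between EVD and the other two could come from the precautions, from a team trained in the skill being measured, from the task (giving medication through an intravenous catheter) or partly from the site (the CDRU is also used for EVD).

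Aim I is meant to identify risk factors for lapses and to inform the Aim II audit tool, so a misattributed risk factor could carry forward.

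**Working it through.** The protocol gives no alpha, power, effect size or within-person correlation for Aim I, so there is no stated figure to reproduce. The correlation ρ is therefore an assumption (0.3, 0.5, 0.7), with a two-sided nominal 5% level.

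**1. HCP type (between people, three groups, m runs each).** The variance of a group mean is inflated by DEFF = 1 + (m − 1)ρ. A three-group test has 2 degrees of freedom and a 5% critical value of 5.991, so the true type I error is about exp(−5.991 / (2 × DEFF)).

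| m | ρ | DEFF | Type I error |
|---|---|---|---|
| 4 | 0.3 | 1.9 | exp(−1.577) = 21% |
| 4 | 0.5 | 2.5 | exp(−1.198) = 30% |
| 4 | 0.7 | 3.1 | exp(−0.966) = 38% |
| 2 | 0.5 | 1.5 | exp(−1.997) = 14% |

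A simulation checked this: 2,000 replicates, normal outcome, no true effect, 120 non-CDRT people with 4 runs and 30 CDRT people with 2. The ANOVA type I error was 20%, 29% and 35% at the three correlations, and Kruskal-Wallis gave 19%, 28% and 36%. At ρ = 0.5, splits of 100/50 and 130/20 gave 29% and 31% for the ANOVA. An ANOVA on person means gave about 5%.

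**2. Contact versus Droplet (within people).** The true variance of the contrast is (1 − ρ) times what the unpaired test assumes, so the standard error is overstated by 1/√(1 − ρ). Take an effect that a paired test would detect with an assumed 80% power, so that effect/true SE = 1.960 + 0.842 = 2.802. The unpaired test rejects only when the estimate exceeds 1.960/√(1 − ρ) true standard errors, so power = Φ(2.802 − 1.960/√(1 − ρ)).

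| ρ | SE overstated by | Power |
|---|---|---|
| 0.3 | 1.20 | Φ(2.802 − 2.343) = 68% |
| 0.5 | 1.41 | Φ(2.802 − 2.772) = 51% |
| 0.7 | 1.83 | Φ(2.802 − 3.578) = 22% |

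In the simulation, the type I error of this unpaired comparison fell to 2.0%, 0.6% and 0%. Within-person differences restored about 5%.

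**3. Duration.** If each volunteer does both lengths, step 2 applies. If each does only one length, in both Contact and Droplet, duration becomes a between-person factor with two runs each. At ρ = 0.5 the two-group type I error is then 2 × (1 − Φ(1.960/√1.5)) = 11%, so the error goes the other way.

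**4. EVD.** With no effect of precaution type, ρ = 0.3 and the 120/30 split, suppose CDRT members differ through training alone by an assumed 0.3 or 0.5 SD. The three-way ANOVA then rejects in 47% or 89% of simulated studies. More subjects would not help, because no one is observed under both EVD and another precaution type.

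**5. Fisher's test.** The number of lapses is a count, and the same paragraph also expresses it per minute. It is a poor example of a categorical outcome.

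**The case against.** **The tests might be meant in paired form, or a statistical analysis plan might correct them.** Student's t-test and ANOVA have paired and repeated-measures versions. But the named alternatives, rank sum and Kruskal-Wallis, are independent-sample tests, and the protocol justifies them by the number of groups. This is unsuitable text rather than silence, and a later plan could not undo the EVD confounding.

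**Aim I is largely descriptive.** This stands. The analysis opens with description, states no hypothesis, primary contrast or power, and no p-value gates Aim II, where the audit tool goes to expert review and field testing. It limits the seriousness of the point but does not make the tests suitable.

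**The magnitudes rest on assumed correlations.** This also stands. The direction of each error does not depend on the value chosen, provided the correlation is positive.

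**Stronger readings that the text does not support.**
- A reader might infer that scenario order is not randomised, and that volunteers learn the powder sites after their first inspection. The protocol says nothing about order, and it states: "Subjects will be blinded to the locations of powder placement". It does not say that volunteers are shown their results between runs.
- A reader might infer that a lower lapse rate under EVD precautions would be due to training. It could equally reflect the PPE, the task or the site. Only non-separability is supported.
- Both durations per person is implied by the reference to A to D but not stated, so the direction of the duration error is conditional.

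**Conclusion.** The point holds and should be corrected. The tests named for Aim I do not fit repeated runs on the same volunteers.

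- **HCP type:** type I error about 20% to 38% for assumed correlations of 0.3 to 0.7 with 4 runs per person, and about 14% at correlation 0.5 with 2 runs.
- **Contact versus Droplet:** an assumed 80% paired power falls to about 68%, 51% and 22% at correlations 0.3, 0.5 and 0.7.
- **Duration:** the same loss if each volunteer does both lengths, and excess false positives if each does one.
- **EVD:** its contrast with Contact and Droplet is confounded with team, task and partly site. This is a feature of the design and does not depend on the assumed correlation.
- **Fisher's test:** the count example is a minor wording error.

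Because Aim I is mainly descriptive and designates no primary contrast, this does not undermine the Aim as a whole.

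**What to change.** In the Aim I Analysis paragraph, replace the independent-group tests with one of two options:

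1. A Poisson or negative-binomial mixed model with a random intercept per volunteer, fixed effects for scenario, duration and HCP type, and an offset of log(scenario minutes). The offset is essential: without it, equal per-minute rates in 20-minute and 10-minute runs would give a duration ratio of about 20/10 = 2 from exposure alone.
2. Within-person differences for Contact versus Droplet (and for duration where each person does both lengths), and person-mean rates for HCP type.

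Then:

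- State whether each volunteer does both durations.
- Limit the precaution-type test to Contact versus Droplet. Report E versus F within the CDRT, and make any comparison of EVD with the other two descriptive only.
- State the EVD confounding under Limitations.
- Keep Fisher's test for truly categorical outcomes, with allowance for repeated runs, and remove the number of lapses as its example.

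The cost is revised analysis and limitations wording. No extra volunteers or runs are needed.
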